### 6.1.5 Health Care Utilization

Data on resource utilization will be collected prospectively for the index hospitalization and the full follow-up period using standardized case report forms.

### 6.1.6 Unscheduled Visit

Unscheduled visits may occur as clinically warranted, and data will be collected if the unscheduled visit is related to the procedure (as determined by the physician). Data on any imaging, medication (anticoagulant, and antiplatelet medications), AEs and SAEs will also be collected if applicable.

### 6.1.7 Schedule of Events

The schedule of assessments for Arterial Subjects is listed in **Table 3**.

**Table 5: Assessment Schedule for Arterial Subjects**

CIP Activity	Baseline	Index Procedure	Discharge	30 Days Follow-up  (-20 days/+ 30 days)	12 Months Follow-up  (-5 months/+ 1 month)	Unscheduled Visit
Enrollment 	X					
Demographics	X					
Medical history	X					
Medications	X	X	X	X	X	X 
Laboratory assessments						
eGFR	X 					
Serum Creatinine (SCr)	X 					
Blood Urea Nitrogen (BUN)	X 					
Potassium (K)	X 					
Hemoglobin (Hgb)	X 					
Platelets (Plt)	X 					
International Normalized Ratio (INR)	X 					
Prothrombin Time (PT)	X 					
Activated Partial Thromboplastin Time (aPTT)	X 					
Clinical assessment	X 					
Physical exam	X 					
ABI	X 			X 		
Rutherford category	X 			X 		
Imaging assessment - Angiogram		X 				
Imaging assessment – DUS	X 			X 	X 	
QOL (SF-12)	X 			X	X	
Adverse event assessment		X 	X 	X 	X 	X 
Healthcare utilization		X				X
Procedure, treatment information, procedure outcome		X				

 in-office visit is required at 30-day follow-up. A telephone contact or virtual visit is an option only for subject who would otherwise miss the visit due to being unable to complete an office visit

 in-office visit is strongly recommended

 retrospective consent within 5 days of JETi-procedure is permitted

 unscheduled Medications reported in Adverse Event form when applicable

 assessment done within 14 days prior to procedure is acceptable

 ABI (only applicable to lower extremity arterial thrombosis) done within 3 months prior to procedure is acceptable. In emergent ALI cases, missing ABI at baseline will not be considered a protocol deviation

 can be obtained via a non-study physician, including a referring physician; this will not be considered a protocol deviation

 Rutherford assessment (only applicable to lower extremity arterial thrombosis) done within 4 days prior to procedure is acceptable

 includes pre-JETi, post-JETi, and final angiograms

 only applicable for arteriovenous thrombosis

 not applicable for post-procedure consented subjects

 Serious adverse events (SAEs) and device deficiencies must be reported within 3 calendar days of Site becoming aware

## 6.2 Venous Subjects

At baseline, demographic information, medications and a medical history will be collected. Laboratory assessments, up to 14 days prior to the JETi procedure will be recorded, and include estimated glomerular filtration rate (eGFR), serum creatinine (SCr), blood urea nitrogen (BUN), potassium (K), hemoglobin (Hgb), platelets (Plt), prothrombin time (PT), international normalized ratio (INR) and activated partial thromboplastin time (aPTT).

Duplex ultrasound examination will be collected at baseline (up to 14 days prior to JETi procedure), at 30-Day and 12-Month Follow-Up. A vascular ultrasound lab that routinely performs compressibility and venous flow on venous cases is recommended. Thrombus obstruction and location will be assessed by venous compressibility with incomplete compression indicating the presence of thrombus in that venous segment. Refer to the DUS core laboratory guidelines for detailed information. All DUS completed are requested to be transmitted to the core lab for analysis.

The pre-JETi venogram will be used to assess the initial degree of clot burden after catheter insertion into the venous system and prior to JETi Thrombectomy. The post-JETi Thrombectomy venogram will be used to assess removal after JETi Thrombectomy and prior to any adjunctive therapies used to treat underlying culprit lesions. The final venogram will be completed to assess clot removal after JETi Thrombectomy and any/all adjunctive therapies and prior to removal of the vascular sheath. All treated vessels will be assessed using the grades in **Table 1**. All venograms will be transmitted to the core lab for review and adjudication.

The Villalta scale is a clinical severity score for the post-thrombotic syndrome (PTS). The Villalta PTS assessment rates the severity of 5 patient-reported symptoms (pain, cramps, heaviness, paresthesia, pruritus) and 6 clinician-observed signs (edema, skin induration, hyperpigmentation, pain during compression, venous ectasia, redness) of PTS on a 4-point scale (0 = none, 1 = mild, 2 = moderate, 3 = severe) for treated limb(s). The Villalta PTS assessment will follow standard scoring completed by the physician. In addition, several patient outcomes will be assessed, including patient-reported Villalta PTS (same timepoints as physician-scored Villalta). The assessment will be collected at baseline (up to 4 days prior to JETi procedure), 30 days, and 12 months.

Severity of leg pain, assessed using a 7-point Likert scale (1 = no pain, 2 = very mild pain, 3 = mild pain, 4 = moderate pain, 5 = severe pain, 6 = very severe pain, 7 = extremely severe pain) will be collected at Baseline, Discharge, 30 days, and 12 months.

The Short Form (SF-12) is a self-reported outcome quality of life measure. Its completion is required at baseline, 30 days, and 12 months. For post-procedurally consented subject, a baseline SF-12 will not be collected as the validity of this assessment is not supported when collected retrospectively.

Anticoagulants, and antiplatelet medications will be collected for this Registry at Baseline Discharge, and all follow-up timepoints. Thrombolytics used during index procedure will be collected. At Baseline, the

---

medications taken within the 30 days prior to the admission and those medications that the patient was taking upon admission will be documented.

AEs experienced by the patient during the study will be reported, please refer to AE reporting section 7.3.1 for additional details of event reporting.

The schedule of events for venous subjects is located in **Section 6.2.7**  
Data collection at each timepoint is discussed in the sections below.

### 6.2.1 Baseline

Subject preparation will occur in accordance with standard hospital policy for the care of interventional endovascular procedures. Note that no data will be recorded until consent is obtained. The following data will be collected:

[figure not shown]
- Enrollment
- Demographics – including date of birth (for US subjects only)/age, sex, race/ethnicity
- Medical history – subject medical history including general medical history, surgical history, vascular history, renal history, deep vein thrombosis history, and thrombotic condition
- Medications: anticoagulant, antiplatelet, and thrombolytic medications (if applicable) taken within the 30 days prior to admission
- Laboratory assessments (within 14 days prior to the JETi procedure):
  - eGFR
  - Serum Creatinine (SCr)
  - Blood urea nitrogen (BUN)
  - Potassium (K)
  - Hemoglobin (Hgb)
  - Platelets (Plt)
  - International normalized ratio (INR)
  - Prothrombin time (PT)
  - Activated partial thromboplastin time (aPTT)
- Clinical assessment – clinical assessment information including height, weight, blood pressure, heart rate, temperature, and respiratory rate
- Physical exam
- Villalta PTS assessment (at baseline or within 4 days prior to JETi procedure)\*
- DUS (within 14 days prior to JETi procedure)\*  
*\* can be obtained via a non-study physician, including a referring physician; this will not be considered a protocol deviation*
- Quality of life (QoL) questionnaire: SF-12 (not applicable for post-procedure consented subjects)
- Leg pain assessment by 7-point Likert Scale

### 6.2.2 Index Procedure

The thrombectomy procedure with the JETi System should be conducted in accordance with standard of care practice and approved labelling. All consented subjects that have a successful or attempted (with at least the JETi Catheter being introduced into the intended vasculature) procedure with the JETi System will be considered registered subjects and will be entered into the study.

The following procedural data will be collected:

- **Procedure information** (including, but not limited to): Start and end dates/times, amount of contrast used during the entire procedure, access sites, obstruction location, and the number of sessions within the procedure (If multiple sessions were needed, the location of the subject in between the sessions is requested.), procedure outcome.
- **Treatment information:** The treatments performed during the index procedure will be captured in the order of performance with specific details for each treatment. The treatment options will include the following:
  - JETi mechanical thrombectomy (MT) only
  - JETi in combination with one or more of the following treatments [REDACTED]

- **Imaging Assessments**
  - Pre-JETi venogram: The pre-JETi venogram will be used to assess the initial degree of clot burden after catheter insertion into the vascular system and prior to JETi thrombectomy.
  - Post-JETi venogram: The post-JETi thrombectomy venogram will be used to assess clot removal after JETi thrombectomy and prior to any adjunctive therapies used to treat underlying culprit lesions.
  - Final venogram: The final venogram will be completed to assess the degree of clot removal after JETi thrombectomy and any/all adjunctive therapies and prior to removal of the vascular sheath.

All treated venous vessels for lower extremity DVT will be assessed using Marder score, per core lab assessment.

- **Acute success, [REDACTED], core laboratory assessed:**
  - Device success: Post-JETi thrombus removal grade II-III, [REDACTED]
  - Technical success: Final thrombus removal grade II-III, [REDACTED] where final [REDACTED] evaluation occurs after JETi system and any other adjunctive device or procedures.

- Procedural success: Technical success with no JETi-related MAEs within 5 days of registration or by discharge, whichever occurs first
- **Adverse events**
- **Medications:** Anticoagulant, antiplatelet, and thrombolytic medications administered during the procedure; anticoagulant and antiplatelet treatments within the peri-operative period should follow recommended societal guidelines.

### 6.2.3 Discharge

Discharge is defined as the subject leaving the treating or referral hospital. Discharge will be performed per standard of care. The following data will be collected:

- Adverse events
- Medications: Anticoagulant, and antiplatelet medications
- Leg pain assessment by 7-point Likert Scale

### 6.2.4 Follow-up (Office Visit)

A window of 10 days to 60 days post JETi procedure is allowed for the 30-day follow-up visit (30 days - 20 days/+30 days), and a window of 7 months to 13 months is allowed for the 12-month (12 months -5 months/+1 month) follow-up visit.

- An in-office visit is required for 30-day and 12-month follow-up visit. If all attempts to have the patient return to the office for an in-office visit are unsuccessful, a phone call follow-up will be allowed to collect applicable data. Protocol deviations will need to be reported for data that could not be collected via phone.

The following data will be collected at the follow-up visit:

- Adverse events
- Medications: Anticoagulant and antiplatelet medications
- Leg pain assessment by 7-point Likert Scale
- DUS \*
- Villalta PTS assessment \*
- QoL questionnaire: SF-12 \*

*\* can be obtained via a non-study physician, including a referring physician. This will not be considered a protocol deviation*

### 6.2.5 Health Care Utilization

Data on resource utilization will be collected prospectively for the index hospitalization and the full follow-up period, including any unscheduled visits, using standardized case report forms.

### 6.2.6 Unscheduled Visit

Unscheduled visits may occur as clinically warranted, and data will be collected if the unscheduled visit is related to the procedure (as determined by the physician). Data on any imaging, clinical assessment, medication (anticoagulant, antiplatelet), and AEs will be collected if applicable.

### 6.2.7 Schedule of Events

The schedule of assessments for Venous Patients is listed in **Table 6**.

**Table 6. Assessment Schedule for Venous Subjects**

CIP Activity	Baseline	Index Procedure	Discharge	30 Days Follow-up  (-20d days/+30 days)	12 Months Follow-up  (-5 months/+1 month)	Unscheduled Visit
Enrollment 	X					
Demographics	X					
Medical history	X					
Medications	X	X	X	X	X	X 
Laboratory assessments						
eGFR	X 					
Creatinine	X 					
Blood Urea Nitrogen (BUN)	X 					
Potassium	X 					
Hemoglobin	X 					
Platelets	X 					
International Normalized Ratio (INR)	X 					
Prothrombin Time (PT)	X 					
Activated Partial Thromboplastin Time (aPTT)	X 					
Clinical assessment	X 					
Physical exam	X 					
Villalta PTS assessment	X 			X	X	
Leg pain assessment (7-point Likert scale)	X		X	X	X	
Imaging assessment						
Venogram		X 				
Duplex ultrasound	X			X	X	
QOL (SF-12)	X 			X	X	
Adverse event assessment		X 	X 	X 	X 	X 
Health care utilization		X				X
Procedure, treatment information, procedure outcome		X				

 In-office visit is required. A telephone contact or virtual visit is an option only for subject who would otherwise miss the visit due to being unable to complete an office visit

 retrospective consent within 5 days of JETi-procedure is permitted

 unscheduled Medications reported in Adverse Event form when applicable

 assessment done within 14 days prior to procedure is acceptable

 assessment done within 4 days prior to procedure is acceptable

 includes pre-JETi, post-JETi, and final venograms

 not applicable for post-procedure consented subjects

 Serious adverse events (SAEs) and device deficiencies must be reported within 3 calendar days of Site becoming aware

### 6.3 Imaging Core Laboratory

An independent core laboratory will be used in this registry to assess the arteriograms/venograms, and DUS imaging submitted by the sites.

## 7.0 ADVERSE EVENTS

To comply with worldwide standards and guidelines on clinical investigation adverse event reporting, the Sponsor has adopted uniform and worldwide applicable standard definitions and reporting timelines to be used and adhered to by the investigators.

### 7.1 Definition

#### 7.1.1 Adverse Event

An adverse event (AE) is any untoward medical occurrence, unintended disease or injury, or untoward clinical signs (including abnormal laboratory findings) in subjects, users or other persons, whether or not related to the medical device under investigation.

As part of ISO14155 Section 3.2, the Adverse Event definition has the following notes:

**Note 1:** This definition includes events related to the medical device under investigation or the comparator.

**Note 2:** This definition includes events related to the procedures involved.

**Note 3:** For users or other persons, this definition is restricted to events related to medical devices under investigation.

#### 7.1.2 Serious Adverse Event

If the AE meets any of the criteria below, it is regarded as a serious adverse event (SAE).

- a) Led to a death,
- b) Led to a serious deterioration in health of the subject, that either resulted in
  1. a life-threatening illness or injury, or
  2. a permanent impairment of a body structure or a body function, or
  3. in-patient hospitalization or prolongation of existing hospitalization, or
  4. medical or surgical intervention to prevent life threatening illness or injury or permanent impairment to a body structure or a body function.
  5. chronic disease
- c) Led to fetal distress, fetal death or a congenital abnormality or birth defect.

**Note:** A planned hospitalization for a pre-existing condition, or a procedure required by the CIP without a serious deterioration in health, is not considered to be an SAE.

### 7.1.3 Device Deficiency/Device Malfunction

Device deficiency is defined as an inadequacy of a medical device related to its identity, quality, durability, reliability, safety or performance, such as malfunction, misuse or use error and inadequate labeling. This includes the failure of the device to meet its performance specifications or otherwise perform as intended. Note: performance specifications include all claims made in the labeling of the device.

A device malfunction is the failure of a device to meet its performance specifications or otherwise perform as intended, when used in accordance with the instructions for use or CIP.

## 7.2 Device Relationship

Determination of whether there is a reasonable possibility that the JETi System caused or contributed to an AE is to be **determined by the Investigator** and recorded on the appropriate case report (CRF) form. Determination should be based on the assessment of temporal relationships, evidence of alternative etiology, medical/biologic plausibility and patient condition (pre-existing condition).

## 7.3 Adverse Event and Device Deficiency/Device Malfunction Reporting

### 7.3.1 Adverse Event Reporting

Safety surveillance and reporting starts as soon as the JETi catheter is introduced into the intended vasculature during the procedure. AEs will not be collected for screen failure subjects. Safety surveillance and reporting will continue until sites perform the last follow-up visit, the subject is deceased, the subject concludes participation in the registry, or the subject withdraws from the registry. Sites will collect all serious adverse events, all JETi device related adverse events, including deaths and device deficiency data throughout the period defined above and will report these events to the Sponsor on a CRF. Sites should update additional information regarding an adverse event on the appropriate CRF.

[figure not shown]
Unchanged, chronic, non-worsening or pre-existing conditions are not AEs and should not be reported.

[figure not shown]
The Sponsor will provide an offline form to allow the investigator to report SAEs in the event the entry cannot be made in the electronic data capture (EDC). This does not replace the EDC reporting system. Sites must still enter all information in the EDC system as soon as feasible.

For the purposes of this Registry, the following adverse events will be reported for each subject through the 12-month follow-up visit.

- All device- and procedure-related AEs
- All SAEs

In addition, the following adverse events regardless of seriousness or relatedness will be collected:

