#### 3.1 **Clinical Investigation Procedures and Follow-up Schedule**

The study flowchart is shown in **Figure 1**, and the follow-up requirements are described in this Section. After meeting all eligibility criteria, a subject is considered enrolled in the registry from the moment the subject provides written informed consent. The point of registration in the registry is when a JETi Catheter is introduced into the intended vasculature of an enrolled subject during the procedure (Day 0). A subject who is enrolled but not registered in this study will be considered a screen failure. Consenting up to 5 days after the JETi procedure is acceptable. In these cases, the point of registration will be the same and any procedural information will be entered post-consent, and adverse events (AEs) will be collected retrospectively from the point of registration (Day 0). Any assessments performed prior to consent will be conducted per standard of care and data collection will occur after consent is obtained. Any assessment performed after consent will be conducted per the protocol's requirements. Registered subjects' data will be collected at baseline, procedure, and discharge, as well as at 30 days (-20 days/+30 days), and 12 months (-5 months/+1 month) after the JETi procedure.

For all follow-up visits, if all attempts to have the patient return to the office for an in-office visit are unsuccessful, a phone call or virtual follow-up will be allowed to collect available data. Protocol deviations must be reported for data that could not be collected via phone.

Refer to the detailed follow-up schedules in **Section 6.1.6** and **6.2.6**.

Figure 1: Study Flowchart

\*Consenting up to 5 days after the JETi procedure is acceptable.

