## 4.2 Descriptive Endpoints

### 4.2.1 All Subjects:

- Procedure-related death as adjudicated by a CEC.
- JETi-related AEs collected at discharge, 30 days, and 12 months follow-up, and as adjudicated by a CEC.
- Procedure-related access site complications such as hematoma, pseudoaneurysm (false aneurysm), perforation, as adjudicated by a CEC.
- Treatment Used: The number and percentage of patients having each of the following treatments:
  - JETi mechanical thrombectomy only
  - JETi in combination with one or more of the following treatments:

- Short-Form Health Survey-12 (SF-12) at baseline, 30-day and 12-month follow-up.

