## 6.0 TREATMENT AND EVALUATION OF ENDPOINTS

For this Registry, the following definitions apply:

- **Index procedure:** the entire intervention to treat the subject's peripheral vascular thrombosis. A subject's procedure may include more than one session if the subject is removed from the interventional suite and placed in a holding area with the intention of returning to the suite for additional treatments either the same day or following day (e.g., catheter placement or removal for CDT). An index procedure can start with JETi or any other treatment first.
- **Treatment:** the individual techniques performed during a procedure to address the subject's peripheral vascular thrombosis (e.g., JETi thrombectomy, balloon angioplasty, stent placement, or catheter-directed thrombolysis (CDT)). Note that "JETi treatment" will refer to treatment during which the JETi Thrombectomy device is used.

NOTE: A subject's treatment is determined by the treating physician based on the clinical situation and institutional practices.

- **Session:** a session is the in and out period within an interventional suite that a subject is receiving treatment. A subject's procedure may include more than one session if the subject is removed from the interventional suite and placed in a holding area with the intention of returning to the suite for additional treatments either the same day or following day (e.g., catheter placement or removal for CDT).

---

 Specifically Lower Extremity DVT subjects as defined in Appendix II

NOTE: Treatment for unexpected re-thrombosis is an adverse event and should not be considered as an additional session of the initial procedure.

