2.0 ANALYSIS CONSIDERATIONS

2.1 Analysis Populations

All registered subjects will be included in the analyses. The point of registration in the Registry is when a JETi Catheter is introduced into the intended vasculature of an enrolled subject during the procedure (Day 0). A subject who is enrolled but not registered in this study will be considered as a screen failure.

[figure not shown]
Consenting up to 5 days post-JETi procedure is acceptable. In these cases, the point of registration will be the same and any procedural information will be entered post-consent, and adverse events (AEs) will be collected retrospectively from the point of registration (Day 0).

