3.2 Adverse Events

All device-, and procedure-related adverse events and all serious adverse events will be summarized for all registered subjects in this trial in terms of the number of events, the percentage of subjects with events.

Statistical Analysis Plan

3.3 **Subject Early Termination**

Subject early termination reasons including deaths, withdrawals, lost-to-follow-up, etc. will be summarized at all scheduled visits.

3.4 **Protocol Deviation**

Protocol deviations will be summarized for subjects in whom a protocol deviation was reported.

4.0 **DOCUMENTATION AND OHER CONSIDERATIONS**

All analyses will be performed using SAS® for Windows, version 9.4 or higher.

Statistical Analysis Plan

5.0 **ACRONYMS AND ABBREVIATIONS**

Acronym or Abbreviation	Complete Phrase or Definition
ABI	Ankle Brachial Index
ALI	Acute Limb Ischemia
AV	Arteriovenous
CDT	Catheter Directed Thrombolysis
CEC	Clinical Events Committee
CIP	Clinical Investigation Plan
DVT	Deep Vein Thrombosis
IVC	Inferior Vena Cava
MAE	Major Adverse Event
OUS	Outside of US
PE	Pulmonary Embolism
PG	Performance Goal
PTS	Post Thrombotic Syndrome
QOL	Quality of Life
SAE	Serious Adverse Event
SAP	Statically Analysis Plan
SF-12	Short-Form Health Survey-12
TIMI	Thrombolysis in Myocardial Infarction
TIPI	Thrombo-aspiration in Peripheral Ischemia

Statistical Analysis Plan

6.0 **REFERENCES**

2. SAS Institute Inc. 2015. SAS/STAT® 14.1 User's Guide. Cary, NC: SAS Institute Inc.

7.0 **APPENDICES**

Statistical Analysis Plan

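### Adverse event collection starts at JETi catheter introduction, but the index procedure can begin earlier, so procedure-related access-site complications and event summaries can be understated

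*Protocol*

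**What the plan says.** **The collection window.** Protocol 7.3.1 states: "Safety surveillance and reporting starts as soon as the JETi catheter is introduced into the intended vasculature during the procedure". It then has sites collect SAEs, JETi-related AEs, deaths and device deficiencies "throughout the period defined above and will report these events to the Sponsor on a CRF". The start coincides with registration: "The point of registration in the registry is when a JETi Catheter is introduced into the intended vasculature of an enrolled subject" (Protocol 3.1). For subjects who consent up to 5 days after the procedure, SAP 2.1 reaches back no further: "adverse events (AEs) will be collected retrospectively from the point of registration (Day 0". Protocol 3.1 has the same rule.

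**The procedure.** Protocol 6.0 defines the index procedure as "the entire intervention to treat the subject's peripheral vascular thrombosis". It allows more than one session, on the same or the following day, and adds: "An index procedure can start with JETi or any other treatment first".

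**What is reported.** Protocol 4.2.1 lists a descriptive endpoint for all subjects: "Procedure-related access site complications such as hematoma, pseudoaneurysm (false aneurysm), perforation, as adjudicated by a CEC". SAP 1.4.2.1 repeats it. SAP 3.2 adds: "All device-, and procedure-related adverse events and all serious adverse events will be summarized for all registered subjects". Protocol 7.3.1 also has a separate list, through 12 months, that names device- and procedure-related AEs and SAEs and gives no starting point.

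**The concern.** The window is tied to the device, while the outputs are tied to the procedure. Vascular access always comes before the JETi catheter reaches the intended vasculature, and in some subjects an entire earlier treatment does too. An access-site perforation at sheath placement, or a bleed during a first session of catheter-directed thrombolysis, belongs to the index procedure but arises before the window opens.

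At stake is whether rates labelled procedure-related describe the whole procedure. If early events are dropped, or are entered at some sites and not at others, the rates are biased downward by an amount that cannot be recovered from the data. The shortfall would also fall unevenly. Subjects treated with JETi first lose only the steps up to catheter introduction, whereas subjects who began with another treatment can lose a full session. Because the registry tabulates JETi alone and JETi in combination with other treatments, a reader could compare groups whose events were captured over different portions of the procedure.

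**Working it through.** No figure in the plan bears on this point, so the check sets the rules side by side and follows each type of event through them.

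1. *Start of the window.* Protocol 7.3.1, Protocol 3.1 and SAP 2.1 all give JETi catheter introduction (Day 0). No visible text in either document sets an earlier start.
2. *Start of the procedure.* Under Protocol 6.0 this is the start of the whole intervention. It can precede Day 0 by the access and preparatory steps, or by a session held the same day or the day before.
3. *SAE before JETi introduction, registered subject.* The sentence in 7.3.1 that limits collection to the defined period names SAEs. Read as written, the event is outside the window.
4. *Non-serious procedure-related AE before JETi introduction.* That sentence does not name this class. The separate list in 7.3.1 does, without a start. Protocol 6.1.2 and 6.2.2 and Tables 5 and 6 place AE assessment at the index procedure. A site could therefore enter the event or omit it. The instruction in 7.3.1 not to report pre-existing conditions adds to the doubt, since a hematoma already present at JETi introduction could be taken as pre-existing.
5. *Event that first arises or worsens after JETi introduction.* Inside the window. This includes access-site complications at or after sheath removal, because the final angiogram or venogram is taken before the sheath comes out.
6. *Procedure-related death.* Captured. A registered subject was alive at JETi introduction, so the death falls inside the window even if its cause arose earlier.
7. *Primary MAE composites and procedural success.* These count only JETi-related events (Protocol 4.1.1, 4.1.2, 4.2.2 and 4.2.3). An event before the catheter was introduced can hardly be JETi-related, so they are essentially unaffected.

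*Size.* Let p be the share of subjects whose procedure began with another treatment. Let q be their probability of a procedure-related event before JETi introduction that is not entered. Let r be the probability that such a subject also has a later event that is counted. These subjects lower the percentage of subjects with events by p × q × (1 − r), and the JETi-first subjects add a similar term for the access step. The documents give none of p, q or r, so no number follows. The count of events loses the early events whatever r is.

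**The case against.** The strongest reply is that non-collection is not proven. The list in 7.3.1 has an end but no start, and AE assessment is scheduled at the index procedure, which is the entire intervention. A site could fairly read this as covering the whole procedure. In addition, the list of events collected regardless of seriousness or relatedness is not visible in the public text, and the CRFs and the CEC charter are separate documents. This stands for non-serious procedure-related AEs: the defect there is an ambiguity, not a demonstrated gap. It does not dispose of SAEs, which the windowed sentence names, and nothing visible points to an earlier start.

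A second reply is that starting at device introduction is a reasonable choice for a device registry and matches the analysis population. That is fair for JETi-related events. It does not justify reporting procedure-related rates under a label wider than the window.

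Three stronger readings are tempting and are not supported:

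- *That all CEC-adjudicated procedure-related endpoints are understated.* Procedure-related death is not.
- *That the loss amounts to a stated number of percentage points.* Any such range would rest on assumed inputs alone.
- *That the loss differs by site.* The documents say nothing about site practice. They support a difference by order of treatment, and the possibility that sites interpret the rule differently.

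**Conclusion.** The point holds as an inconsistency between the collection window and the outputs that depend on it. Following the stated start rule truncates two outputs: the descriptive endpoint of procedure-related access-site complications, and the SAP 3.2 summary of procedure-related AEs and SAEs. The direction is downward, and the effect is concentrated in subjects whose procedure began with another treatment. For JETi-first subjects only the steps up to catheter introduction are lost, which should be a small effect.

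The size cannot be stated from the documents. Neither output is part of a primary endpoint, so this should be corrected but does not threaten the registry's main safety conclusion. The judgement assumes that sites follow 7.3.1 as worded and that the text not visible here sets no earlier start.

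**What to change.** In Protocol 7.3.1 and 3.1 and in SAP 2.1, state that for registered subjects procedure-related AEs and SAEs are collected from the start of the index procedure, meaning first vascular access of the first session, retrospectively where needed. State also that JETi-related AEs are counted from JETi catheter introduction. Leave Day 0 and the exclusion of screen failures unchanged.

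Because a subject whose procedure stops before JETi remains a screen failure, the report should note that the resulting rate is conditional on reaching JETi introduction.

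If the sponsor prefers the current window, the alternative is to relabel the access-site endpoint (Protocol 4.2.1, SAP 1.4.2.1) and the SAP 3.2 summary as events from JETi introduction onward, and to give the list in 7.3.1 the same explicit start.

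The cost of the first option is low. Procedure start dates and times and the order of treatments are already recorded (Protocol 6.1.2 and 6.2.2), and retrospective AE entry is already used for subjects consented afterwards, although only back to Day 0. Expect a small amount of extra data entry, a note in the CRF completion instructions, and possibly slightly higher procedure-related rates. The second option needs only wording changes.
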